at the UPenn site will enter the variables into the randomization program, which will assign a randomization group to the participant; 3) the designated study staff member will fax the participant's randomization group to IDS, which will assign a kit number to the participant and fax the kit assignment to the research coordinator; 4) the research nurse or physician will dispense medication to the participant and complete and sign the IDS prescription form included in the starter kit; 5) The research coordinator will fax the completed form to IDS. The medication will be dispensed using the above dosing schedule. To maintain double-blind conditions, study staff responsible for randomization will not be involved in the recruitment of participants, study visits, or data collection. IDS will provide each study site a supply of starter kits to use for initial study medication dispensing.

Study drug for subsequent visits will be ordered by the research coordinator using the "Research Pharmacy Schedule" form, a copy of which will be retained in the participant's research file. The study drug will be ordered at Baseline Visit B for Weeks 2-5 and Target Quit Day Visit C for Weeks 6-10. The study drug will be picked up at IDS and brought to the study visit. If the participant is unable to attend the scheduled study visit the study drug will be stored at the Treatment Research Center in the Medication Room. Study drug will be dispensed at three time points during the study: Baseline (Visit B: 1 week of medication), Target Quit Date (Visit C: 4 weeks of medication), and Week 5 (Visit E: 5 weeks of medication). The initial dispensing will be done directly by the research nurse or physician, who will ensure that the patient understands the medication regimen. Study medication will be dispensed by the research nurse, physician, or research coordinator (trained and supervised by the nurse or physician), who will assess each participant for study medication AEs, documenting and reporting them as required. Participants with severe psychological symptoms or determined to be inappropriate for the study by an investigator will be withdrawn from the study. A study nurse or physician will follow participants withdrawn completely from treatment until they are referred for appropriate clinical care. For research purposes, and with the participant's continued approval, we will collect data at all subsequent time points until the 24 weeks post-TQD visit.

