Although this session requires an in-person visit, part of the session may be completed via telephone. The session must be completed 1-30 days after completion of the screening visit. At the in-person visit, we will measure breath CO level and draw three tubes (i.e., 21 cc) of maternal blood to assess NMR and provide DNA for genotyping. Blood will be stored in a coded manner in a designated -80° freezer and shipped on dry ice to the laboratory of [name] at the University of Toronto approximately every four months throughout the study. Samples from both sites will be shipped from their storage location at Penn (see section 9.5) and will follow the guidelines for shipping international biological samples as required by the university.

Table 2: Study Assessments

	Visit A	Visit B	Visit C	Visit D	Visit E	Visit F	Visit G	Visit H	Visit I	Visit J
	Screen	Baseline (Pre-quit)	Wk 1 (TQD)	Wk 3	Wk 5	Wk 7	Wk 10	Wk 24	Wk 2 PP	Wk 6 PP
ICF with HIPAA	X									
Medical record review	C									
Med History Questionnaire	X									
Demographics	X									
SORT	X									
MINI 	X				X 		X 			
TLFB (preceding 30 days)	X									
Gestational Age	X, C									
Blood sample: DNA, NMR		X								
Breath CO*	X	X	X		X		X	X 		
Dispense medication		X	X		X					
Text messaging		Daily	Daily	Daily	Daily	Daily	Daily			
Assessment of AEs and medication adherence		X	X	T	X	T	X			
Weight, blood pressure	X or C	C	C	C	C	C	C			
Pulse		X	X		X		X			
ACE questionnaire		X or T								
Smoking History Questionnaire		X or T								
FTND		X or T								
BISS		X or T								
WEAQ		X or T								
PHQ-9	X	X or T	X	T	X	T	X	X	T	T
QSU		X or T	X		X		X			
MED-Q							X			
TLFB (since last visit)		X or T	X	T	X	T	X	X	T	T

CONFIDENTIAL

This material is the property of the University of Pennsylvania. Do not disclose or use except as authorized in writing by the study sponsor

Smoking cessation counseling (30 min)		X							
Smoking cessation counseling (20 min)			X						
Smoking cessation counseling (10 min)				T	X			T	T
Blood sample: [bupropion, hydroxybupropion]					X				
Birth outcome data								C	

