TQD: target quit date; PP: postpartum; ICF: informed consent form; HIPAA: Health Insurance Portability and Accountability Act; Assessments: X=in-person; X=MINI sections A through K will be administered. X=Only MINI section B (Suicidality) will be administered; X=in-person only; T=by telephone; C=chart review; SORT: Slosson Oral Reading Test; MINI: Mini-International Neuropsychiatric Interview; TLFB: Timeline Follow-back Interview for cigarettes smoked; NMR: nicotine-metabolite ratio; [CO]: carbon monoxide concentration; AEs: adverse events FTND: Fagerstrom Test for Nicotine Dependence; BISS: Body Image State Scale; PHQ-9: Patient Health Questionnaire-9; WEAQ: Weight Efficacy After taken Quitting survey; QSU: Questionnaire of Smoking Urges; MED-Q: medication group question; \*CO readings may also be at the time of delivery and at the time of the post-partum office visit

An in-person or telephone interview will be used to obtain background information for use as potential covariates and to assess the study's external validity [including smoking history (e.g., age at initiation, past use of nicotine treatments, current rate, menthol vs. regular tobacco, presence of other smokers in the home), obstetrical history to confirm and augment information obtained from review of the medical record (number of pregnancies, pregnancy outcomes), and medical and psychiatric history (with current medications extracted from the medical chart). Sessions in which the assessments are conducted by telephone, the telephone interview should be completed prior to the in-person visit.

Nicotine dependence severity will be assessed with the Fagerstrom Test for Nicotine Dependence, a validated 6-item measure (144). We will measure depression symptom score using the PHQ-9 (145) and will use a score of 10 or more to differentiate depressed and non-depressed women. This cut point will enable us to use depression as a stratification variable and potential mediator. Craving severity, which has been related to long-term cessation in cessation trials (147), will be measured with the 10-item brief Questionnaire of Smoking Urges (QSU; 146). The QSU contains 2 subscales (anticipation of reward, relief from negative affect).

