#### **6.5 Visit D: Week 3 (Approximately 25 minutes by telephone or in person)**

Participants will be asked to complete the PHQ-9 and the TLFB by telephone. They will then receive a 10-minute booster counseling session that focuses on reinforcing success and reviewing the quit plan (for participants who have quit smoking) or re-establishing a quit date

CONFIDENTIAL

and restarting the cessation process (for participants who have relapsed to smoking). The counseling schedule reflects the changing needs of the pregnant smoker during the course of pregnancy and smoking cessation (155), with more intensive help offered in the earliest phase of treatment and continued efforts to prevent relapse in the later stages.

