#### **6.6 Visit E: Week 5. (Approximately 30 minutes in-person)**

At the in-person visit, we will measure breath CO level, and participants will meet with a study nurse or coordinator working under the supervision of the nurse or physician to receive a five-week supply of study medication. The nurse or coordinator will review with the participant instructions for taking the study medication and record any AEs that the participant may have experienced. The nurse or coordinator will also collect empty medication blister packs and any unused medication. Two tubes of blood (14 cc) will be drawn at this visit for shipment to [name] laboratory at the University of Toronto to measure plasma concentrations of bupropion and hydroxybupropion. Participants will be asked to complete PHQ-9, QSU, and TLFB, either in person or by telephone. They will then receive a 10-minute booster counseling that focuses on reinforcing success and reviewing the quit plan (for participants who have quit smoking) or re-establishing a quit date and restarting the cessation process (for participants who have relapsed to smoking). Suicidal risk will be assessed using the MINI Suicidality section (B).

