#### **6.7 Visit F: Week 7. (Approximately 15 minutes by telephone or in person)**

Participants will be asked to complete the PHQ-9 and TLFB by telephone.

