#### **6.8 Visit G: Week 10 (Endpoint). (Approximately 25 minutes in-person)**

At the in-person visit, we will measure breath CO level. The nurse or coordinator (trained and supervised by the nurse or physician) will review with the participant any AEs that the participant may have experienced. The nurse or coordinator will also collect empty medication blister packs and any unused medication. Participants will be asked to complete the PHQ-9, QSU, MED-Q, and TLFB in-person. Suicidal risk will be assessed using the MINI Suicidality section (B).

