### **7.2.3. Specific Aim 2: Assess changes in depression symptoms and craving as mediators of bupropion's effect on quit rates.**

We will use a regression-based path model approach to examine mediation of treatment effects based on MacKinnon et al. (175). All variables will be standardized for the analyses. The two suspected mediators will be entered as standardized pre-post differences, continuously distributed and treated as normal in linear regression. The effects of treatment arm on

CONFIDENTIAL

mediators, and of mediators on outcome, will be assessed using linear regression and standardized variables. We will focus on changes in mediators from baseline to week 3, since abstinence-induced withdrawal effects typically peak within the first 3 weeks of cessation (174), but we can examine delayed changes to weeks 5, 7, and 10 as well. Assuming that treatment predicts our mediators, we will then assemble the path model using standard structural equation modeling approaches. The path model partitions the effect of treatment on outcome into direct (and unexplained) effects vs. mediated effects. We will then test the overall mediation hypothesis using the proportion of treatment effect explained (171-172), and the strength of each mediating pathway. To do this, we will estimate the model for standardized treatment predicting abstinence without mediators to estimate the direct effect of treatment in the unadjusted model ( $\hat{\beta}^{\dagger}$ ). We will then test whether treatment predicts each of the suspected mediators and, in turn, test whether mediators predict abstinence in an adjusted treatment model and estimate the effect of treatment in the mediator adjusted model  $\hat{\beta}^*$ . Finally, we will calculate the proportion of treatment effect explained, which is calculated as  $(\hat{\beta}^{\dagger} / \hat{\beta}^*)$ ; the standard error for this quantity is calculated using the delta method, and the mediation hypothesis will be tested using a z-test. Individual pathways will be tested using products of the coefficients along each path using a delta-method based z-test.

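### Aim 2 centres on mediator change to week 3, but the only craving scale is not scheduled at week 3 or week 7, so craving mediation can be run at only two of the four named windows

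*Combined protocol and SAP*

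**What the plan says.** Section 7.2.3 enters two mediators, change in depression symptoms and change in craving, as standardized pre-post differences. On timing it states: "We will focus on changes in mediators from baseline to week 3". The reason given is that withdrawal effects usually reach their height in the first three weeks after quitting. Changes to weeks 5, 7 and 10 are offered as further looks.

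Section 6.3 names the craving instrument: craving severity "will be measured with the 10-item brief Questionnaire of Smoking Urges (QSU; 146"). No other craving scale is scheduled anywhere.

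The schedule is in "Table 2: Study Assessments". Its QSU row is filled at Visits B (baseline), C (week 1, the target quit day), E (week 5) and G (week 10), and is blank at Visits D (week 3) and F (week 7). The PHQ-9 row is filled at all ten visits.

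The visit descriptions agree with the table:
- **Week 1 (6.4):** the QSU is included.
- **Week 3 (6.5):** "Participants will be asked to complete the PHQ-9 and the TLFB by telephone".
- **Week 5 (6.6):** "Participants will be asked to complete PHQ-9, QSU, and TLFB, either in person or by telephone".
- **Week 7 (6.7):** "Participants will be asked to complete the PHQ-9 and TLFB by telephone".
- **Week 10 (6.8):** "Participants will be asked to complete the PHQ-9, QSU, MED-Q, and TLFB in-person".

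**The concern.** The analysis text and the assessment schedule do not match. A baseline-to-week-3 craving change needs a QSU score at week 3, and none is planned. One of the two mediating pathways therefore has no data at the window the plan puts first.

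Aim 2 is a Specific Aim with its own power statement in 7.1.2, where the type I error is set at 0.025 for two pathways. That correction covers two mediators. It does not cover a choice of craving window made after the data are in. If 7.2.3 stays as it is, that choice will have to be made later.

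The windows that remain for craving also fit the plan's purpose less well. Week 5 falls after the early-withdrawal period that motivated week 3. Week-10 craving is collected at the visit that determines week-10 abstinence.

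**Working it through.** The plan gives no figure to reproduce here. The check sets the windows named in 7.2.3 against the Table 2 rows and the visit text.

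**Step 1. Availability at each visit.** Week 1 is the target quit day, so days from the quit day = 7 × (week − 1).

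| Visit | Week | Days from quit day | PHQ-9 (Table 2) | QSU (Table 2) | Named window in 7.2.3 |
|---|---|---|---|---|---|
| B | baseline | before quit day | X or T | X or T | reference point |
| C | 1 | 7 × 0 = 0 | X | X | no |
| D | 3 | 7 × 2 = 14 | T | blank | yes, the focus |
| E | 5 | 7 × 4 = 28 | X | X | yes |
| F | 7 | 7 × 6 = 42 | T | blank | yes |
| G | 10 | 7 × 9 = 63 | X | X | yes |

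Visits A, H, I and J have a PHQ-9 entry and no QSU entry. X is in person and T is by telephone.

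**Step 2. Count over the four named windows.**
- PHQ-9: weeks 3, 5, 7 and 10, so 4 of 4.
- QSU: weeks 5 and 10, so 2 of 4.
- Both mediators at the same window: 2 of 4.

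**Step 3. Check the day count.** Section 5.3 lists the supply given at "Target Quit Date (Visit C: 4 weeks of medication") and five weeks' supply at Visit E. That is 28 days to Visit E, then 35 more to Visit G: 28 + 35 = 63, as in the table.

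**Step 4. The gap in craving measurement.** Section 6.12 sets a target window of 3 days either side of each scheduled date. The post-baseline QSU readings then fall at:
- Week 1: day 0, range −3 to 3.
- Week 5: day 28, range 25 to 31.
- Week 10: day 63, range 60 to 66.

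No QSU is scheduled from day 4 to day 24. Apart from the quit-day visit itself, the first 21 days of cessation have no craving measure. A week-3 reading would fall at day 14, range 11 to 17.

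**Step 5. Could week 3 mean three weeks after the quit day?** That would be day 21, about study week 4. No QSU falls between weeks 1 and 5, so this reading does not help.

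**Step 6. Order relative to the outcomes.** Section 3.2 defines abstinence over at least the 7 days before the assessment. Week-10 craving is recorded at the end of that period and so does not precede the week-10 outcome. Week 5 is the only named window at which craving is measured before both the week-10 and the 24-week outcomes.

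**Step 7. Could the blanks come from how the table was read?** The QSU and PHQ-9 rows each keep ten cells, and the visit text shows the same pattern. Sections 6.5 and 6.7 are not full lists, since they also omit the adverse-event and adherence check that Table 2 places at those visits. The case therefore rests mainly on the Table 2 row, with the visit text as support.

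**The case against.** The strongest reply is that the plan already has room for this. It speaks of a focus, not an exclusive window, and names weeks 5 and 10, where the QSU is collected. Craving mediation can still be tested. That is true and limits the damage, but a later optional look does not supply the missing week-3 score, and the plan does not say which later window takes over for craving.

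A second reply is that 7.2.3 does not require both mediators to use the same window. A joint model with PHQ-9 change to week 3 and QSU change to week 5 could be fitted from scheduled data. This is correct, and the statement about the joint model applies to a common window. A mixed-window model is still not a model at week 3 or week 7, and the plan does not specify one.

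Third, the order problem at week 10 would apply equally to the PHQ-9 and is not caused by the missing QSU. That stands. It matters here only because craving has a single other window left.

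Fourth, the 3-day window is a target that 6.12 allows to be extended, so the day 4 to day 24 gap describes the schedule and not every participant. This also stands. The count of two windows out of four does not depend on it.

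**Conclusion.** The concern holds. As written, the craving pathway of Aim 2 cannot be analysed at the plan's main window or at week 7. Depression change is available at 4 of the 4 named windows and craving change at 2 of 4. A joint model at a common window is likewise limited to weeks 5 and 10. Week 5 is about four weeks after the quit day, outside the three-week period the plan gives as its reason.

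H1 to H3 and the depression pathway are not affected, and craving mediation remains possible at weeks 5 and 10. This should be fixed, but it does not threaten the primary efficacy result.

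The conclusion assumes that the QSU is the only craving measure and that Table 2 is the operative schedule. The day counts also assume visits near their scheduled dates.

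**What to change.** **Preferred.** Add the QSU to Visits D and F in Table 2 and to sections 6.5 and 6.7. Both contacts already take the PHQ-9 by telephone, and telephone QSU is already allowed at baseline (Table 2), week 1 (6.4) and week 5 (6.6). Visit D matters most because it serves the focal window.

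The cost is 2 × 10 = 20 items per participant on contacts planned at about 25 and 15 minutes, with no new visit. A few extra minutes per call is an assumption, since the documents give no completion time for the QSU. Participants already past Visit D when the change takes effect would have no week-3 score. The documents do not give accrual status. If the change comes part-way through, 7.2.3 should also state in advance how those participants are handled.

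**If week 3 can no longer be added.** Amend 7.2.3 before unblinding to:
1. name week 5 as the pre-specified window for craving and for the joint two-mediator model;
2. state that this is about four weeks after the quit day and so outside the three-week withdrawal period;
3. keep week 3 for the depression-only pathway;
4. remove week 7 for craving.

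This costs a few sentences. Its downside is that craving in early withdrawal is not captured.

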### **7.1.2. Aim 2:**

Analyses here will assess changes in craving and depression symptom scores as mediators of bupropion treatment effects at weeks 10 of treatment and 24 weeks post-TQD. These measures are continuous difference scores. Our sample of 360 is well above the minimum sample of 200 recommended for such analyses (169-170). The mediation hypotheses will examine the proportion of variance in treatment effect explained (171-172), and we will test each mediation hypothesis with a z-score generated using the delta method. Our sample of 360 gives us 80% power to observe small effects in a 1-sample test ( $\delta = 0.16$ ) when testing at  $\alpha = 0.05$ . There are 2 proposed mediating pathways (depression and craving) between treatment and outcome, so our type-1 error will be corrected to 0.025. A sample of 360 gives us 80% power to detect small-to-medium effects ( $\delta=0.35$  SD) for changes in the proposed mediators, which we have seen in previous trials (15, 52).

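### Aim 2 scores its mediators only after the quit day, so its pathway test cannot separate mood or craving driving abstinence from abstinence driving mood or craving

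*Combined protocol and SAP*

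**What the plan says.** **Mediator timing (7.2.3).** "We will focus on changes in mediators from baseline to week 3". The reason for this choice and the later options are given together: "since abstinence-induced withdrawal effects typically peak within the first 3 weeks of cessation (174), but we can examine delayed changes to weeks 5, 7, and"; the list ends with week 10.

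**Quit day.** Table 2 (section 6.3) and section 6.4 place the target quit day at Visit C, week 1. All four named mediator visits come after it.

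**Outcomes.** Section 7.1.2 describes the scores as "mediators of bupropion treatment effects at weeks 10 of treatment and 24 weeks post-TQD". Section 3.2 defines abstinence over at least the 7 days before each assessment, with a CO check.

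**Model (7.2.3).** After testing treatment on each mediator, the plan will "test whether mediators predict abstinence in an adjusted treatment model". Each pathway is then tested by the product of its two coefficients with a delta-method z. Section 7.1.2 corrects the type-1 error to 0.025 for the two pathways. The overall hypothesis is tested separately, by the proportion of treatment effect explained.

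**What is absent.** Smoking status at the mediator visit is not in the model, and no check on temporal order is planned. The covariate rules in 7.2, 7.2.1 and 7.2.2 do not name it either. In context they concern sample characteristics, predictors of missingness and baseline imbalance.

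**Data scheduled (Table 2, 6.4 to 6.8).** PHQ-9 and TLFB are taken at every visit from B to G. QSU is taken at baseline and weeks 1, 5 and 10, but not at week 3 or week 7.

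**The concern.** The hypothesis runs from drug to mood or craving to abstinence. The plan's reason for choosing week 3 implies that an arrow also runs back from abstinence to the score. A woman abstinent at week 3 is more likely than others to be abstinent at week 10. Early abstinence is then a common cause of the mediator score and the outcome, and it is omitted from the model. The mediator slope can be non-zero although the mediator does nothing.

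The direction of the error is not known in advance. If quitting lowers craving or depression, the test can declare mediation that does not exist. If early withdrawal raises them, the spurious association has the opposite sign and can hide real mediation.

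A week-10 mediator paired with the week-10 outcome is the plainest case: the score is taken at Visit G, after the 7-day abstinence window it is meant to explain.

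Mediation is a named specific aim, so its conclusion should be able to tell these readings apart.

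**Working it through.** **1. The plan's own figures.** One-sample test, δ = 0.16, N = 360: Φ(0.16·√360 − 2.241) = Φ(0.794) = 78.7% at two-sided 0.025, close to the stated 80%. At the 0.05 printed in that sentence it is 85.9%. Week-10 quit rates of 21.2% and 35.9% with 180 per arm give 87.3%, against the stated 88%. The point does not depend on these.

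**2. Inputs.** From the documents: 180 per arm (5.3); week-10 quit rates 21.2% and 35.9% (7.1.1); drug effect on the mediator 0.35 SD and α = 0.025 (7.1.2), taken as two-sided (critical value 2.241). Assumed, because the documents give neither: the shift d in the mediator caused by being abstinent, and the carry-over from early to week-10 abstinence. Carry-over is written as the percentage abstinent at week 10 among women abstinent, then not abstinent, at the mediator visit. The true effect of the mediator on abstinence is zero.

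**3. Analytic check (carry-over 70%/8%, d = 0.5).**
- Early abstinence: (0.212 − 0.08)/0.62 = 0.213 on placebo; (0.359 − 0.08)/0.62 = 0.450 on bupropion.
- Mean within-arm variance of early abstinence: (0.1676 + 0.2475)/2 = 0.2075. Covariance with the outcome: 0.62 × 0.2075 = 0.1287.
- Within-arm mediator variance: 1 + 0.5² × 0.2075 = 1.052.
- Spurious slope: 0.5 × 0.1287/1.052 = 0.061.
- Within-arm outcome variance: (0.1671 + 0.2301)/2 = 0.1986, or 0.1947 after the mediator. SE = √(0.1947/(360 × 1.052)) = 0.0227, so z for this path is about 2.70. Taken alone it rejects with probability Φ(2.70 − 2.24) = 68%.
- Treatment-to-mediator path: z = 0.35/√(1.052 × 4/360) = 3.24.
- Product z: 3.24 × 2.70/√(3.24² + 2.70²) = 2.07, just short of 2.241 for a null pathway.

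**4. Simulated rejection of the pathway test, no true mediation.** Linear models, one mediator, total drug effect on the mediator 0.35 SD.

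| Shift d (SD) | 70%/8% | 60%/10% | 50%/12% |
|---|---|---|---|
| 0 | 0.4% | | |
| 0.25 | 5–6% | 4% | 2% |
| 0.5 | 28–30% | 17% | 7–8% |
| 0.75 | 56–58% | | |

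Week-10 mediator with week-10 outcome: 16% at d = 0.25 and 64% at d = 0.5.

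**5. Sensitivity.** Holding early quit rates at 21.2% and 35.9%, and making 0.35 SD the direct rather than the total drug effect, gives 6.8%, 21.9% and 47.5% at d = 0.5 for early-to-week-10 correlations of 0.3, 0.5 and 0.7. At d = 0.2 the figures are 1.2%, 2.4% and 4.8%. If abstinence raises the score instead, rejection is 1.7% to 27.1% over shifts of 0.2 to 0.8 SD and correlations of 0.5 and 0.7.

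**6. Drug acts on the mediator only through quitting (70%/8%).** 0.03%, 1.7% and 10.9% at d = 0.25, 0.5 and 0.75.

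**7. Adjusting for abstinence at the mediator visit.** With no true mediation, rejection falls to 0.3–0.6%. Now let mediation be real and act through early quitting (70%/8%, assumed log-odds 0.7, 1.0 or 1.5 per SD). Power of the planned test is about 50%, 71% and 82%; with the covariate it is under 1% in all three.

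**The case against.** **Post-quit measurement fits the mechanism.** Section 1.1 expects bupropion to work by easing craving during abstinence, so scores taken after quitting are where the effect should appear. This stands. A reader might infer that the week-3 visit is simply mistimed; the documents do not support that, because a week-3 change precedes both outcomes. Order alone does not remove the shared cause, early abstinence.

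**Adjusting for early abstinence may be worse than the bias.** A reader might infer that this covariate is the obvious repair. It is measured after randomization and lies on the hypothesised path, and step 7 shows it can remove nearly all power when mediation is real. It cannot be the main model. Week-3 status would also usually be telephone self-report, since no CO is scheduled then.

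**The size is assumed.** This stands. The documents give neither the abstinence shift nor the carry-over from week 3. The three carry-over settings imply early quit rates on bupropion of 45%, 52% and 63%, against 35.9% expected at week 10. The lowest cell in the table, about 2%, is not above nominal. Large inflation mostly needs a direct drug effect on the mediator. Section 1.1 does expect such effects, and 7.1.2 powers for 0.35 SD.

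**Only part of the test was simulated.** This also stands. The runs used one mediator and the product test, not the overall proportion-explained test.

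**The week-10 change is optional.** It is true that 7.2.3 only permits it and does not tie it to the week-10 outcome. But 7.1.2 lists week 10 as an outcome and nothing rules the pairing out.

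**The quit-day change is not clean either.** Section 6.4 has the Visit C counselling review the first quit attempt, so some women may already have stopped, and only one week of drug has been taken. Both are fair limits.

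**Conclusion.** The concern holds for the Aim 2 pathway analysis. As written, a significant pathway could mean that mood or craving drove abstinence, or that abstinence moved mood or craving. With a 0.35 SD drug effect on the mediator and no true mediation, the test rejects in about 2% to 29% of trials for assumed shifts of 0.25 to 0.5 SD, depending on carry-over, and in 16% to 64% for the week-10 mediator with the week-10 outcome. Stronger carry-over or a larger direct drug effect gives more. If the drug reaches the mediator only through quitting, the rate stays below 2% at those shifts.

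Two stronger readings should be resisted. A reader might infer that any mediation finding here would be false; the calculations show only that its direction would be unproven. A reader might also infer that the efficacy result is affected; the H1 analysis in 7.2.2 does not use the mediators.

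A related limit follows from the visit schedule. With no QSU at week 3 or week 7, the focal craving change cannot be computed. Post-quit craving is left with week 5, or with week 10 for the 24-week outcome.

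**What to change.** In section 7.2.3:

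- **(a) Order.** State that the week-10 mediator change will not be used for the week-10 outcome and is kept for the 24-week outcome only. This secures order, not direction: 7.1.1 puts the correlation between week-10 and week-24 results above 0.7.
- **(b) Quit-day analysis.** Pre-specify an analysis using the change from baseline to week 1 (Visit C) in PHQ-9 and QSU, as the version least affected by quitting. Say that it reflects one week of drug and that some women may already have stopped.
- **(c) Sensitivity analysis.** Report the post-quit analysis also with TLFB abstinence over the 7 days before the mediator visit as a covariate. Label it sensitivity only, and state that it removes any mediation acting through early quitting.
- **(d) Wording.** Describe post-quit mediation results as association that does not establish direction.
- **(e) Craving visits.** State that post-quit craving uses week 5, or week 10 for the 24-week outcome.

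The cost is SAP wording and a few extra model fits, since every measure is already scheduled. The price in information is that the quit-day change may show a smaller drug effect, and so have less power, than a later one. If (b) and (c) disagree with the post-quit analysis, the paper will have to leave direction open.
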